7.1.2 Screening

The clinical screening period starts once a patient has provided written informed consent to participate in the study and ends on the day of study entry. Screening assessments have to be done within 14 days prior to the first dose of INC280. Patients' demographics and other characteristics data to be collected include: general demography, relevant medical history/current medical conditions, diagnosis of HCC, extent of cancer (using BCLC staging classification-[Appendix 3](#)) for study eligibility evaluation, and prior antineoplastic therapies (medication, radiation and surgery), CPC ([Appendix 2](#)), physical examination, height and weight, vital signs, ECOG performance status, cardiac assessment, safety laboratory assessments including hematology, biochemistry, coagulation and pregnancy tests. Other assessments will include the special laboratory assessments such as hepatitis markers. Clinical and radiological tumor assessment by RECIST ([Appendix 1](#)) should be conducted preferably within 1 week (7 days) prior to the first dose of the study drug; however tumor assessments up to 3 weeks (21 days) prior to the first dose will be acceptable. During screening, the disease must be staged. The tumor assessment made during the screening phase will provide the baseline tumor measurements, which will be used to determine future responses and/or progression. A complete list of screening evaluations is provided in the visit of assessments table ([Table 7-1](#)).

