8.1 Adverse events

8.1.1 Definitions and reporting

An AE is defined as the appearance of (or worsening of any pre-existing) undesirable sign(s), symptom(s), or medical condition(s) that occur after patient's signed informed consent has been obtained.

For patients whose c-MET status is unknown and who sign the molecular pre-screening ICF, AEs which occur after signature of this consent will only be captured if they meet the definition of serious as outlined in [Section 8.2](#) and are reported to be causally related with study

procedures (e.g. an invasive procedure such as biopsy). Once the main study ICF is signed, all AEs per the descriptions below will be captured in the AE CRF.

Patients whose c-MET status is known will sign the main study ICF.

Abnormal laboratory values or test results occurring after informed consent constitute AEs only if they induce clinical signs or symptoms, are considered clinically significant, require therapy (e.g., hematologic abnormality that requires transfusion or hematological stem cell support), or require changes in study medication(s).

AEs that begin or worsen after informed consent should be recorded in the AEs CRF. Conditions that were already present at the time of informed consent should be recorded in the Medical History page of the patient's CRF. AE monitoring should be continued for at least 30 days (or 5 half-lives, whichever is longer) following the last dose of study treatment. AEs (including lab abnormalities that constitute AEs) should be described using a diagnosis whenever possible, rather than individual underlying signs and symptoms. When a clear diagnosis cannot be identified, each sign or symptom should be reported as a separate AE.

AEs will be assessed according to the Common Terminology Criteria for AEs (CTCAE) version 4.03.

If CTCAE grading does not exist for an AE, the severity of mild, moderate, severe, and life-threatening, corresponding to Grades 1 - 4, will be used. CTCAE Grade 5 (death) will not be used in this study but is collected as a seriousness criteria; rather, information about deaths will be collected through a Death form.

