The occurrence of AEs should be sought by non-directive questioning of the patient (subject) during the screening process after signing informed consent and at each visit during the study. AEs also may be detected when they are volunteered by the patient (subject) during the screening process or between visits, or through physical examination, laboratory test, or other assessments. As far as possible, each AE should be evaluated to determine:

1. The severity Grade (CTCAE Grade 1-4)
2. Its duration (Start and end dates)
3. Its relationship to the study treatment (Reasonable possibility that AE is related: No, Yes)
4. Action taken with respect to study or investigational treatment (none, dose adjusted, temporarily interrupted, permanently discontinued, unknown, not applicable)
5. Whether medication or therapy was given (no concomitant medication/non-drug therapy, concomitant medication/non-drug therapy)
6. Outcome (not recovered/not resolved, recovered/resolved, recovering/resolving, recovered/resolved with sequelae, fatal, unknown)
7. Whether it is serious, where a SAE is defined as in [Section 8.2.1](#), and which seriousness criteria have been met.

All AEs should be treated appropriately. If a concomitant medication or non-drug therapy is given, this action should be recorded on the AE CRF.

Once an AE is detected, it should be followed until its resolution or until it is judged to be permanent, and assessment should be made at each visit (or more frequently, if necessary) of

any changes in severity, the suspected relationship to the study treatment, the interventions required to treat it, and the outcome.

Progression of malignancy (including fatal outcomes), if documented by use of appropriate method (for example, as per RECIST criteria for solid tumors), should not be reported as a SAE.

AEs separate from the progression of malignancy (example, deep vein thrombosis at the time of progression or hemoptysis concurrent with finding of disease progression) will be reported as per usual guidelines used for such events with proper attribution regarding relatedness to the drug.

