10.5.3.2 Adverse events (AEs)

All AEs recorded during the study will be summarized. The incidence of treatment-emergent AEs (new or worsening from baseline) will be summarized by primary system organ class, severity based on the National Cancer Institute's Common Terminology Criteria for Adverse Events (CTCAE) current edition version 4.03, type of AE, and relationship to the study drug by study Part. Deaths reportable as SAEs and non-fatal SAEs will be listed by patient and tabulated by primary system organ class, type of AE, and study Part.

Qualifying AEs will be separately listed by primary system organ class, worst grade based on the CTCAE current edition version 4 and type of AE. The DDS will be used.

Any other information collected (e.g. start/end dates and duration of AE, severity or relatedness to study medication) will be listed as appropriate. For patients undergoing intra-patient escalation to doses other than their initially received dose level, data up to the first intra-patient escalation will be summarized and all post-escalation data will only be listed.

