1. ***pre-treatment period:*** from day of patient’s first informed consent to the day before first administration of study treatment
2. ***on-treatment period:*** from date of first administration of study treatment to 30 days after date of last actual administration of any study treatment (including start and stop date)
3. ***post-treatment period:*** starting at day 30+1 after last administration of study treatment.

Safety summaries include only data from the on-treatment period with the exception of baseline data which will also be summarized where appropriate (e.g. change from baseline summaries). In particular, summary tables for adverse events (AEs) will summarize only on-treatment events, with a start date during the on-treatment period (**treatment-emergent** AEs).

However, all safety AE data (including those from the pre-treatment period) will be listed.

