2.9.1.3 AE summaries

AE summaries will include all AEs occurring during on-treatment period (Section 2.1.1). All AEs collected in the AE (e)CRF page will be listed along with the information collected on those AEs e.g. AE relationship to study drug, AE outcome etc. AEs starting during the post-treatment period will be flagged in the listings.

AEs will be summarized by number and percentage of patients having at least one AE, having at least one AE in each primary system organ class (SOC) and for each preferred term (PT) using MedDRA coding. A patient with multiple occurrences of an AE will be counted only

once in the respective AE category. A patient with multiple CTCAE grades for the same preferred term will be summarized under the maximum CTCAE grade recorded for the event. AE with missing CTCAE grade will be included in the 'All grades' column of the summary tables.

In AE summaries the SOC will be presented alphabetically and the PTs will be sorted within primary SOC in descending frequency, based on their frequency in the 'All Patients' column.

The following AE summaries will be produced by study treatment group:

- Overview of AE
- AEs regardless of study treatment relationship by SOC, PT and maximum grade
- AEs regardless of study treatment relationship by PT and maximum grade
- AEs suspected to be study treatment related by PT and maximum grade
- SAEs regardless of relationship to study treatment by PT and maximum grade
- SAEs suspected to be study treatment related by PT and maximum grade
- Summary of qualifying AE for dose decision analysis (Dose determining part only)
- AEs leading to discontinuation of study treatment regardless of relationship to study treatment by PT and maximum grade
- AEs leading to discontinuation of study treatment suspected to be study treatment related by PT and maximum grade
- AEs requiring dose adjustment/interruption by SOC, PT and maximum grade
- AEs requiring additional therapy by SOC, PT and maximum grade

Additionally, for the legal requirements of ClinicalTrials.gov and EudraCT, two required tables on on-treatment adverse events which are not serious adverse events with an incidence greater than 5% and on on-treatment serious adverse events and SAE suspected to be related to study treatment will be provided by system organ class and preferred term on the safety set population.

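### SAP 2.1.1 defines treatment-emergent AEs by start date alone and omits the protocol's worsening criterion, so an AE that arises in screening and worsens on INC280 can be missing from the AE tables

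*SAP*

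**What the plan says.** Protocol 10.5.3.2 sets the analysis: "The incidence of treatment-emergent AEs (new or worsening from baseline) will be summarized by primary system organ class", and also by severity, type and relationship to study drug. Worsening from baseline is part of the definition.

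SAP 2.1.1 divides follow-up into three periods. The pre-treatment period runs from the patient's "first informed consent to the day before first administration of study treatment". The on-treatment period runs from first dose to 30 days after last dose. AE tables "will summarize only on-treatment events, with a start date during the on-treatment period", and the SAP attaches the term treatment-emergent to exactly those events. Nothing in the SAP mentions worsening of an event that began earlier. All AEs, including pre-treatment ones, are to be listed.

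SAP 2.9.1.3 refers back to 2.1.1 for all its summaries: the overview, AEs by class and term, SAEs, AEs leading to discontinuation, AEs requiring dose adjustment or interruption, and AEs requiring additional therapy.

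On data collection, protocol 8.1.1 says "AEs that begin or worsen after informed consent should be recorded in the AEs CRF". Conditions present at consent go to the Medical History page instead. Once detected, an AE is reassessed at each visit for "any changes in severity, the suspected relationship to the study treatment, the interventions required to treat it, and the outcome".

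SAP section 4, which records changes from the protocol's analyses, names only the dropped per-protocol analyses.

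**The concern.** The two documents give one term two definitions, and the narrower one drives the tables. AE recording starts before dosing, so some events will carry a pre-treatment start date. If such an event becomes more severe on INC280, the protocol counts it as treatment-emergent. The SAP does not, unless the worsening has a start date of its own.

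Safety is a secondary objective in a single-arm study with small groups, so a single omitted event is visible in an incidence. The tables could also disagree with each other. A patient who stops INC280 because of such an event could appear under AE as the discontinuation reason in the disposition table (SAP 2.3.1, taken from the End of Treatment page), yet be absent from the table of AEs leading to discontinuation.

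**Working it through.** The plan gives no figure to reproduce. The check compares the two rules and applies them to a constructed case.

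1. **Is there a pre-dose window in which AEs are recorded?** Yes. AE recording starts at main consent (protocol 8.1.1), and "Screening assessments have to be done within 14 days prior to the first dose of INC280" (protocol 7.1.2). Under the earlier molecular pre-screening consent, only serious events related to study procedures are captured. The window for ordinary AEs is therefore short, running from main consent to first dose.

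2. **Constructed case.** Use the calendar dates in the SAP 2.1.1 study-day examples, with first dose on 05-Jan-2014. Suppose an AE starts on 02-Jan-2014 at grade 1 and reaches grade 3 on 09-Jan-2014.
   - Day of onset: before first dose, study day = date − first dose = 2 − 5 = −3.
   - Day of worsening: on or after first dose, study day = date − first dose + 1 = 9 − 5 + 1 = 5.

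3. **Apply both rules.**

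| How the event is held | Protocol 10.5.3.2 | SAP 2.1.1 |
|---|---|---|
| One AE record, start day −3, later grade 3 | Counted | Not counted |
| First record from day −3, new record opened on day 5 at grade 3 | Counted | Counted (second record) |
| Condition present before consent (Medical History), worsening entered as an AE starting on day 5 | Counted | Counted |

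Only the first row shows a difference.

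4. **Do the documents say which of the first two rows applies?** No. Protocol 8.1.1 asks for one start and end date per AE and then follows that AE for changes in severity, which fits a single record. SAP 2.9.1.3 also has a rule for merging consecutive records of the same term whatever their severity, which suggests that separate records may exist. Neither passage says what happens to the start date when the grade of an AE already on the eCRF rises.

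5. **Does another SAP rule bring the event back?** No. The rule that shows a patient under the highest grade for a term works only on events that already qualify. The imputation rules (SAP Tables 2-3 and 2-4) place a partial start date of uncertain relation to first dose after first dose. They do not touch an event whose pre-dose start date is known.

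6. **Scale.** Protocol 1.2.1.2.2 gives 8 Dose-Determining and 28 Expansion patients at 28 September 2015. One omitted patient is 1/8 = 12.5 percentage points, or 1/28 = 3.6 percentage points. This shows what one patient weighs; it does not estimate how many are missed. Enrollment continued after that date, and the SAP splits the Expansion patients by formulation, so the final denominators will differ.

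**The case against.** The strongest reply is that separate dated records are the natural reading. Protocol 8.1.1 asks for one grade and one pair of dates per AE, and the SAP's merging rule expects back-to-back records of one term. If each grade increase opens a record, the start-date rule gives the protocol's result. This is plausible and may be what sites did, but no passage requires it. Following an AE for changes in severity is at least as consistent with one continuing record.

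A second reply is that SAP 2.9.1.3 speaks of events occurring in the on-treatment period, which alone might cover an event still ongoing then. It refers back to 2.1.1, however, where the start-date condition is explicit.

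A third reply stands in full: AE tables are not the only display. Laboratory worsening appears in grade shift tables and worst-grade frequencies (SAP 2.9.2), neither of which depends on an AE start date. Dose interruptions and discontinuations with reasons are summarised from dosing data (2.5.2.4), and on-treatment deaths separately (2.9.1.5). The gap is thus mainly in non-laboratory events, since vital signs and ECGs are only listed and physical examination findings stay in source documents.

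A reader might infer something stronger: that the rule undercounts worsening of the liver abnormalities, ascites or fatigue that many of these patients bring into the study. The documents do not support that. Conditions present at consent are Medical History, and the protocol's AE definition includes worsening of a pre-existing condition. Worsening after first dose is then a new AE that would naturally carry an on-treatment start date, so the SAP counts it.

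Finally, the deciding details are outside these documents. The SAP places derived-variable rules in a separate programming specification, and the eCRF layout is not shown. That limits any statement about size. It does not remove the mismatch between the two definitions.

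**Conclusion.** The mismatch is established. The protocol's definition includes worsening, the SAP's does not, the SAP's governs every AE table, and the change is undeclared. The consequence is conditional and narrow. An event is lost only if it first arises between main consent and first dose, worsens on INC280, and is kept under its original start date. Its number cannot be derived from the documents. It is zero if every grade increase has its own dated record, and probably small otherwise because the window is short. The documents do not show that any event has been or will be missed.

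It should still be changed. A stated rule that departs from the protocol's definition and can drop an on-treatment worsening is more than missing detail, and aligning it is cheap. This rests on two assumptions: that sites record pre-consent conditions and their worsening as protocol 8.1.1 describes, and that no specification outside these documents already restores the worsening criterion.

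**What to change.** In SAP 2.1.1, extend the definition of a treatment-emergent AE. After the on-treatment start-date condition add: *or started before treatment and increased in CTCAE grade during the on-treatment period*. Apply it to all summaries in 2.9.1.3, including SAEs and AEs leading to discontinuation, using dated grade records where the eCRF holds them.

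If the eCRF opens a new dated record at each grade increase, no new derivation is needed. State that rule in 2.1.1, so that a reader can see that the start-date criterion delivers the protocol's definition. If the eCRF provides neither a dated grade history nor separate records, the worsening cannot be derived from AE data, and the narrower definition should be declared in SAP section 4.

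The cost is one sentence, one derivation comparing the on-treatment grade with the pre-dose grade, and slightly higher AE counts.

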2.2 Analysis sets

Full Analysis Set

The Full Analysis Set (FAS) comprises all patients who received at least one dose of INC280. The FAS will be used for all listings of raw data. Unless otherwise specified the FAS will be the default analysis set used for all analyses.

Safety Set

The Safety Set includes all patients from the FAS who have received at least one dose of INC280 and had at least one valid post-baseline safety assessment.

Please note: A “**no**” to indicate that the patient had no AEs (on the AE eCRF) constitutes a valid safety assessment.

Per-protocol Set

Not applicable. As the study did not meet the planned enrollment, supportive analysis with PPS is no longer of clinical interest.

Dose-determining analysis set

The dose-determining set (DDS) consists of all patients from the safety set (who are in the Dose-Determining Part) who either meet the minimum exposure criterion and have sufficient safety evaluations (as determined by the Investigators and Novartis), or who have experienced a qualifying AE during the first four weeks of treatment.

A patient is considered to have met the minimum exposure criterion at a dose level if they receive INC280 at the planned dose, BID for at least 21 days within the first four weeks of treatment ($\geq 75\%$ planned administration). Patients who do not experience a qualifying AE during the first four weeks are considered to have sufficient safety evaluations if they have been observed for ≥ 28 days following the first dose, and are considered by both the Sponsor and Investigators to have enough safety data to conclude that a qualifying AE did not occur.

Pharmacokinetic analysis set

The pharmacokinetic analysis set (PAS) consists of all patients who provide an evaluable PK profile. A profile is considered evaluable if all of the following conditions are satisfied:

- Subject receives one of the planned treatments
- Subjects provides at least one primary PK parameter
- Subject did not vomit within 4 hours after the dosing of INC280

2.2.1 Subgroup of interest

Analyses of efficacy data may be presented separately for patients meeting the revised definition of c-MET positive, as introduced in Protocol Amendment 2; i.e. MET gene copy number ≥ 5 by FISH with c-MET IHC intensity score +2 in $\geq 50\%$ of tumor cells or unknown, or c-MET IHC intensity score +3 in $\geq 50\%$ of tumor cell or presence of c-MET mutation.

The primary and secondary endpoints (refer to [Section 1.2](#)) will be performed based on FAS. For more information please refer to [Section 2.7.1](#).

2.3 Patient disposition, demographics and other baseline characteristics

Summaries and listings described in this section will be done by study treatment groups based on the FAS.

2.3.1 Patient disposition

The FAS will be used for the patient disposition summary tables and listings. The following will be tabulated:

- Number (%) of patients who are still on-treatment (based on non-completion of the 'End of Treatment Disposition' page),
- Number (%) of patients who discontinued treatment (based on completion of the 'End of Treatment Disposition' page with discontinuation date and reason entered),
- Primary reasons for study treatment discontinuation (based on discontinuation reason entered in the 'End of Treatment Disposition' page),
- Number (%) of patients who complete study evaluation (based on completion of the 'End of Post-treatment follow-up' page with discontinuation date and reason entered),
- Primary reasons for study evaluation completion (based on discontinuation reason entered in the 'End of Post-treatment follow-up' page),

Treatment/study completion status and the reason for discontinuation from study will be listed, along with dates of first and last study drug treatment, duration of exposure to study drug treatment and date of discontinuation for each patient.

2.3.2 Basic demographic, Prognostic factors for HCC and background data

Demographic data including age, sex, race, ethnicity, height, baseline weight, body mass index (BMI), ECOG(WHO) performance status, HBV/HCV at diagnosis, Child Pugh, alpha fetoprotein, portal vein invasion at diagnosis and distant metastases at diagnosis will be listed and summarized. In addition, child bearing potential and pregnancy test results will be listed, and age (18 - <65, 65 - <85, ≥ 85 years) and weight (<55 , $55-75$, ≥ 75 kg) categories will be summarized.

BMI is calculated using the following formulas:

- BMI [kg/m²] = weight[kg] / (height[m]**2)

2.3.3 Medical History

Relevant medical history and current medical conditions will be listed using Safety set..

2.3.4 Prior antineoplastic therapy

Concomitant medications will be coded using the WHO Anatomical Therapeutic Chemical (ATC) dictionary using the latest version available prior to clinical database lock.

All concomitant medications will be listed using Safety set, with a flag to differentiate those which started more than 30 days after the last study treatment.

